5.2. Handling of Adverse Events

Multiple episodes of the same AE/ADR (SOC) in the same patient will be tabulated as 1 patient.

Multiple episodes of the same AE/ADR (PT) in the same patient will be tabulated as 1 event.

For tabulation by type (seriousness, time of onset, outcome), multiple episodes of the same AE/ADR (PT) in the same patient will be tabulated as 1 event on a PT basis according to the following order of precedence:

Seriousness: serious > not serious

Time of onset: chronological order

Outcome: death > recovered with sequelae > not recovered > recovering > recovered > unknown

5.3. Handling of Missing Data

In principle, no missing data will be imputed.

For frequency tabulation of qualitative variables, missing data will be handled as “unknown,” and the column of “unknown” will not be presented if there is no relevant patient. For summary statistics of quantitative variables, missing data will be excluded.

5.4. Handling of Time Points of Assessment

Data within the permissible range as shown below will be employed.*

If there are multiple pieces of data within the permissible range, data on the day closest to the nominal day will be employed. If deviation is the same before and after the nominal day, the latest data will be employed.

Data collected up to the end date of Benet/Actonel treatment* + 30 days will be employed for bone

turnover markers and low back pain, and data collected up to the end date of Benet/Actonel treatment* + 90 days will be employed for the other endpoints. For patients with interruption of treatment, no data collected after 3 consecutive months (90 days) of interruption will be used for (efficacy) analysis.

At the final assessment, the latest available data (excluding data before the start of treatment) will be employed.

The start day of Benet/Actonel treatment is designated as Day 1, and the previous day as Day -1.

* Specified in Section 5.5, “Derived Variables”

<Time points of assessment of bone turnover markers and low back pain>

| Time point of assessment | Permissible range | Nominal day |
|-------------------------------|-------------------|-------------|
| Before the start of treatment | Days -30 to 1 | Day 1 |
| Month 3 | Days 2 to 135 | Day 90 |
| Month 6 | Days 136 to 270 | Day 180 |
| Month 12 | Days 271 to 450 | Day 360 |
| Month 18 | Days 451 to 630 | Day 540 |
| Month 24 | Days 631 to 810 | Day 720 |
| Month 30 | Days 811 to 990 | Day 900 |
| Month 36 | Days 991 to 1170 | Day 1096 |
| Final assessment | Days 2 to 1170 | - |

<Time points of assessment of bone mineral density>

| Time point of assessment | Permissible range | Nominal day |
|-------------------------------|-------------------|-------------|
| Before the start of treatment | Days -90 to 30 | Day 1 |
| Month 3 | Days 31 to 135 | Day 90 |
| Month 6 | Days 136 to 270 | Day 180 |
| Month 12 | Days 271 to 450 | Day 360 |
| Month 18 | Days 451 to 630 | Day 540 |
| Month 24 | Days 631 to 810 | Day 720 |
| Month 30 | Days 811 to 990 | Day 900 |
| Month 36 | Days 991 to 1170 | Day 1096 |
| Final assessment | Days 31 to 1170 | - |

<Time points of assessment of height>

| Time point of assessment | Permissible range | Nominal day |
|--------------------------|-------------------|-------------|
| | | |

| | | |
|-------------------------------|------------------|----------|
| Before the start of treatment | Days -90 to 1 | Day 1 |
| Month 12 | Days 2 to 450 | Day 360 |
| Month 24 | Days 451 to 900 | Day 720 |
| Month 36 | Days 901 to 1170 | Day 1096 |
| Final assessment | Days 2 to 1170 | - |

5.5. Derived Variables

| Derived variable | Description |
|---|---|
| Flag for enrollment | It is identified whether a patient is enrolled. |
| Flag for CRF collection | It is identified whether the CRF for a patient is collected. |
| Flag for inclusion in/exclusion from safety | It is identified whether a patient is evaluated for safety. |
| Flag for inclusion in/exclusion from efficacy | It is identified whether a patient is evaluated for efficacy. |
| Flag for inclusion in/exclusion from vertebral fracture | It is identified whether a patient is evaluated for vertebral fracture. |
| Age (years) | Age on the start day of Benet/Actonel treatment; or age described on the [Cover] in the CRF for Actonel Tablets if age cannot be calculated due to missing data on date of birth |
| BMI (kg/m ²) | Body mass index calculated as body weight (kg) ÷ height (m) ² |
| Duration of disease (years) | Number of years from diagnosis of osteoporosis to the start date of Benet/Actonel treatment (by rounding down) |
| Start date of Benet/Actonel treatment | The earliest (smallest) date among dates described in the [Treatment status of Benet/Actonel] in the CRF and when a patient appears to have taken the drug |
| End date of Benet/Actonel treatment | 30 days after the latest (largest) date among dates described in the [Treatment status of Benet/Actonel] in the CRF and when a patient appears to have taken the drug |
| Duration of Benet/Actonel treatment (days) | Number of days from the start date of Benet/Actonel treatment to the end date of Benet/Actonel treatment “End date of Benet/Actonel treatment” - “start date of Benet/Actonel treatment” + 1 |
| Duration of Benet/Actonel treatment (months) | Number of months from the start date of Benet/Actonel treatment to the end date of Benet/Actonel treatment “Duration of Benet/Actonel treatment (days)” ÷ 30 |

| Derived variable | Description |
|--|--|
| Number of doses of Benet/Actonel | 
Number of doses during Benet/Actonel treatment counted as the number of checks made to “Took the drug on the day indicated by a physician” or “Took the drug on a different day from instructed by a physician” for patient’s treatment status in the [Treatment status of Benet/Actonel] in the CRF
 
Data are collected in the [Treatment status of Benet/Actonel] in the CRF on a dose basis (first dose, second dose, third dose,.....) for Benet and on a monthly basis (Month 1, Month 2, Month 3,.....) for Actonel. For tabulation, data of Actonel will be handled on a dose basis in line with data of Benet. No month with blank will be counted.
 |
| Amount of Benet/Actonel administered (mg) | Total dose during Benet/Actonel treatment calculated as number of doses of Benet/Actonel \times 75 mg |
| Treatment rate (%) | Number of doses of Benet/Actonel \div number of entered “date indicated by a physician” |
| Treatment compliance rate (%) | Percentage of the number of doses taken as instructed by a physician relative to the number of doses indicated by the physician calculated as the number of checks made to “Took the drug on the day indicated by a physician” \div number of entered “date indicated by a physician” |
| Dosing interval (days) | 
Number of days from the date of a certain dosing to the date of the next dosing
 
“Date of the next dosing” - “date of a certain dosing”
 
Date of dosing refers to date when a patient took the drug (records of “Took no dose” for patient’s treatment status are excluded to identify “date of a certain dosing” and “date of the next dosing”). Dosing interval is missing if either date of dosing is missing.
 |
| Duration of use (days) | 
Number of days from the start date of Benet/Actonel treatment to the end date of Benet/Actonel treatment
 
“End date of Benet/Actonel treatment” - “start date of Benet/Actonel treatment” + 1
 |
| Duration of interruption of treatment (days) | 
Number of days from the date of a certain dosing to the date of the next dosing
 
“Date of the next dosing” - “date of a certain dosing”
 |

| Derived variable | Description |
|--|--|
| | Date of dosing refers to date when a patient took the drug (records of “Took no dose” for patient’s treatment status are excluded to identify “date of a certain dosing” and “date of the next dosing”). Dosing interval is missing if either date of dosing is missing. |
| Flag for previous treatment | A drug deemed as previous treatment is identified. Previous treatment being used after the start of Benet/Actonel treatment is also identified with a flag for concomitant medication. |
| Flag for concomitant medication | A drug deemed as concomitant medication is identified. Concomitant medication that has been used since before the start of Benet/Actonel treatment is also identified with a flag for previous treatment. |
| Flag for osteoporosis drug | An osteoporosis drug is identified. |
| Flag for anti-inflammatory analgesic | An anti-inflammatory analgesic is identified. |
| Flag for cardiovascular drug | A cardiovascular drug is identified. |
| Flag for central nervous system drug | A central nervous system drug is identified. |
| Flag for antidiabetic | An antidiabetic is identified. |
| Flag for digestive system drug | A digestive system drug is identified. |
| Flag for other drug | Other drug not listed above is identified. |
| Flag for Benet/Actonel 2.5 mg | A drug that is Benet/Actonel 2.5 mg is identified. |
| Flag for Benet/Actonel 17.5 mg | A drug that is Benet/Actonel 17.5 mg is identified. |
| Flag for bisphosphonate other than Benet/Actonel | A bisphosphonate other than Benet/Actonel is identified. |
| Flag for calcium | A drug that is calcium is identified. |
| Flag for vitamin D | A drug that is vitamin D is identified. |
| Flag for osteoporosis drug not listed above | A drug that is an osteoporosis drug not listed above is identified. |
| Flag for steroid | A drug that is a steroid is identified. |
| Flag for parathyroid hormone | A drug that is a parathyroid hormone is identified. |
| Flag for anti-RANKL | A drug that is an anti-RANKL monoclonal antibody is |

| Derived variable | Description |
|--|--|
| monoclonal antibody | identified. |
| Number of days to measurement (days) | Number of days from the start date of Benet/Actonel treatment to the date of measurement of the relevant endpoint “Date of measurement” - “start date of Benet/Actonel treatment” + 1; or “date of measurement” - “start date of Benet/Actonel treatment” if the date of measurement is earlier than the start date of Benet/Actonel treatment |
| Time point of assessment (for analysis) | Time points of assessment of bone turnover markers, low back pain, bone mineral density, and height are reallocated for analysis as specified in Section 5.4, “Handling of Time Points of Assessment.” |
| Flag for employment of data | It is identified whether measurement data are employed. |
| Flag for event | A patient with event is defined as a patient who experienced at least one event such as vertebral fracture. A patient with no event is defined as a patient who experienced no event. |
| Time point of event onset | Time point of event onset is defined as the first onset of event such as vertebral fracture. Patients with no event are censored at the final assessment. |
| Measured value before the start of treatment | The measured value before the start of treatment is identified. |
| Change | Value obtained by deducting the measured value before the start of treatment from a measured value at each time point |
| Percent change (%) | Value obtained by dividing a change by the measured value before the start of treatment and then multiplying the division by 100 |
| Time of onset (days) | Number of days from the start date of Benet/Actonel treatment to the date of onset of AE “Date of onset” - “start date of Benet/Actonel treatment” + 1 |
| Flag for inclusion/exclusion as an AE | It is identified whether an event is an AE. |
| Relationship (for analysis) | It is identified whether an AE is related to Benet/Actonel. The causal relationship is handled as specified for “Adverse drug reaction” in Section 3.2. |
| Seriousness (for analysis) | It is identified whether an AE is serious. The seriousness is |

| Derived variable | Description |
|-------------------------------|--|
| | handled as specified for “Serious adverse event” in Section 3.2. |
| Novelty | It is identified whether an AE is expected (known) or unexpected (unknown) based on the precautions for Benet/Actonel. |
| Presence or absence of an AE | It is identified whether there is an AE (including “unknown”). |
| Presence or absence of an ADR | It is identified whether there is an ADR (including “unknown”). |
| Presence or absence of a SAE | It is identified whether there is a SAE (including “unknown”). |

6. Analysis Plan

Analysis sets, analysis items, and analysis methods are shown below. Details of variables for analysis and display will be specified in separately prepared statistical analysis specifications.

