6.3.1. Incidence of Vertebral Fracture

| | |
|---------------------|--|
| 1) Analysis set | Patients evaluated for efficacy with dates of pre- and post-treatment ^{*1} radiography Patients evaluated for vertebral fracture |
| 2) Chart plan | Table 3-1-1-1 Table 3-1-1-2 Table 3-1-1-3 Table 3-1-1-4 Table 3-1-1-5 Table 3-1-1-6 Table 3-1-2-1 Table 3-1-2-2 Table 3-1-2-3 Table 3-1-2-4 Table 3-1-2-5 Table 3-1-2-6 |
| 3) Analysis items | New vertebral fracture or worsening of prevalent fracture New vertebral fracture or worsening of prevalent fracture <non-traumatic> New vertebral fracture New vertebral fracture <non-traumatic> Worsening of prevalent fracture Worsening of prevalent fracture <non-traumatic> |
| 4) Analysis methods | For the time to the first onset of the analysis item, the point estimate of cumulative incidence, standard error, and 95% confidence interval will be calculated using the Kaplan-Meier method, and the number of relevant patients (number of patients at risk), cumulative number of patients with |

the analysis item, and cumulative number of censored patients at Month 6 (Day 180), Month 12 (Day 360), Month 18 (Day 540), Month 24 (Day 720), Month 30 (Day 900), and Month 36 (Day 1096) will be calculated. In addition, a Kaplan-Meier curve will be plotted with the cumulative incidence (%) on the vertical axis and the time (months) on the horizontal axis. The number of relevant patients (number of patients at risk) will be presented under the time (months).

The time to the first onset of the analysis item is defined as time from the start date of Benet/Actonel treatment to the earliest date of radiography with a diagnosis of the analysis item. Patients with no analysis item will be censored at the latest date of radiography with no evidence of the analysis item.^{*2}

No radiographic data collected after the end date of Benet/Actonel treatment + 90 days or after 3 consecutive months (90 days) of interruption in patients with interruption of treatment will be used for analysis.

*1 Range of assessment before and after treatment

- Before treatment: before the start of Benet/Actonel treatment defined as Days -90 to 1
- After treatment: before the end date of Benet/Actonel treatment + 90 days, and before 3 consecutive months (90 days) of interruption in patients with interruption of treatment

*2 The date of radiography with no evidence of the analysis item is defined as follows for each analysis set:

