6.3.2. Incidence of Non-vertebral Fracture

| | |
|---------------------|---|
| 1) Analysis set | Patients evaluated for efficacy |
| 2) Chart plan | Table 3-2-1 Table 3-2-2 Table 3-2-3 Table 3-2-4 |
| 3) Analysis items | Non-vertebral fracture Non-vertebral fracture <non-traumatic> Femur fracture Femur fracture <non-traumatic> |
| 4) Analysis methods | Non-vertebral fracture will be analyzed in the same manner as described in Section 6.3.1, “Incidence of Vertebral Fracture.” The time to the first onset of the analysis item is defined as time from the start date of Benet/Actonel treatment to the earliest date of diagnosis of the analysis item. Patients with no analysis item will be censored at the latest date of dosing, discontinuation, assessment of each efficacy endpoint, or onset/outcome of AE. |

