6.3.3. Incidence of Vertebral Fracture Event at Each Time Point of Assessment

| | |
|---------------------|--|
| 1) Analysis set | Patients evaluated for vertebral fracture |
| 2) Chart plan | Table 3-3-1 Table 3-3-2 |
| 3) Analysis items | New vertebral fracture or worsening of prevalent fracture New vertebral fracture or worsening of prevalent fracture <non-traumatic> |
| 4) Analysis methods | The number of relevant patients, observed person·years, number of patients with the first onset of the analysis item, and incidence rate (number of patients with event/100 person·years) in the range of assessment at each time point of assessment (see below) will be calculated, and the ratio of incidence rate at each time point of assessment relative to Month 6 and its 95% confidence interval will be calculated. Handling of onset day of the analysis item and data for analysis will be as specified in Section 6.3.1, “Incidence of Vertebral Fracture.” |

Observed person·years: (1)+2)) ÷ 12

1): (Number of patients with radiography, no event, and no censoring in the range of assessment at each time point of assessment) \times 6

A patient with no radiography at the relevant time point of assessment, but with valid radiography at any later time point will be counted at the relevant time point of assessment.

2): Total time (months) from the start date of assessment to event or censoring in the range of assessment at each time point of assessment for patients with event or censoring

Incidence rate: (number of patients with event \div observed person-years) \times 100

Range of assessment at each time point of assessment

| Time point of assessment | Range of assessment |
|--------------------------|---------------------|
| Month 6 | Days 2 to 180 |
| Month 12 | Days 181 to 360 |
| Month 18 | Days 361 to 540 |
| Month 24 | Days 541 to 720 |
| Month 30 | Days 721 to 900 |
| Month 36 | Days 901 to 1096 |

No radiographic data collected after the end date of Benet/Actonel treatment + 90 days or after 3 consecutive months (90 days) of interruption in patients with interruption of treatment will be handled as data in the range of assessment (not used for analysis).

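### Vertebral films, bone density and height measured 91 to 120 days after a dose are kept or dropped according to whether the patient later restarts, because the two data cut-offs start 30 days apart.

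*SAP*

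**What the plan says.** Section 5.5 of SAP v5.1 sets the end date of treatment at "30 days after the latest (largest) date among dates described in the [Treatment status of Benet/Actonel] in the CRF", counting only doses the patient appears to have taken. Treatment duration is the "Number of days from the start date of Benet/Actonel treatment to the end date of Benet/Actonel treatment", so the 30 days after the last dose count as treatment. The row for duration of interruption in the same table reads "Number of days from the date of a certain dosing to the date of the next dosing". That row, its formula and its note on missing dates are the same as in the dosing-interval row.

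Two cut-offs use these quantities. Section 5.4 allows a period after treatment ends: "data collected up to the end date of Benet/Actonel treatment* + 90 days will be employed for the other endpoints". The other endpoints are those apart from bone turnover markers and low back pain, which get 30 days. Section 5.4 then adds: "For patients with interruption of treatment, no data collected after 3 consecutive months (90 days) of interruption will be used for (efficacy) analysis". Section 6.3.1 repeats both limits for vertebral radiographs in its text and in note *1 ("before 3 consecutive months (90 days) of interruption in patients with interruption of treatment"). Section 6.3.3 does the same: "No radiographic data collected after the end date of Benet/Actonel treatment + 90 days or after 3 consecutive months (90 days) of interruption".

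**The concern.** The primary endpoint is vertebral fracture, timed and censored by the date of the radiograph. A rule on which radiographs count should depend on what has happened up to the film. Here two patients with the same dosing history up to the film can be treated differently because of what one of them does afterwards.

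A dropped film can remove a fracture or move a censoring date back. If it was the first film after the start of treatment and the later ones are also dropped, criterion 4 of section 4.5 takes the patient out of the vertebral fracture set. Bone density and height are exposed to the same rule.

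**Working it through.** The SAP states no cut-off in days from the last dose, so there is no figure to reproduce. Let L be the last dose taken before the gap.

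**1. Status of the 30 days.** After a single dose, end date = start + 30 and treatment duration = 30 + 1 = 31 days. The interruption formula, next dose minus previous dose, starts at L and so counts the same 30 days as interruption.

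**2. Cut-offs in days after L.**

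| Endpoint | Never restarts | Restarts after a triggering gap | Rules disagree on |
|---|---|---|---|
| Vertebral radiographs, bone density, height | 30 + 90 = 120 | 90 | days 91 to 120 |
| Bone turnover markers, low back pain | 30 + 30 = 60 | 90 | days 61 to 90 |

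Note *1 of section 6.3.1 says before rather than up to. On that wording the first window is days 90 to 119, still 30 days.

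**3. Two patients with the same exposure before the film.** Last dose Day 271, film Day 371.
- Never restarts: the limit is 271 + 30 + 90 = Day 391, so the film is used.
- Restarts on Day 380: the gap is 380 − 271 = 109 days and the limit is 271 + 90 = Day 361, so the film is dropped.

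With interruption counted from L + 30, the second gap is 109 − 30 = 79 days. The rule is not triggered and the film is used.

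**4. Where the trigger falls.** For dose dates from 1 May 2013 to 31 July 2017 (1,553 dates), two missed monthly doses give a calendar gap of 89 to 92 days and three give 120 to 123. Less 30, these become 59 to 62 and 90 to 93. Assume the restart date varies evenly by up to 7 days either way. The share of gaps that trigger the rule is then (limit ≥ 90 / > 90):

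| Missed doses | Now | Counted from L + 30 |
|---|---|---|
| Two | 62.3% / 55.7% | 0% / 0% |
| Three | 100% / 100% | 65.3% / 58.6% |

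**5. How many films.** The documents give no missed-dose rates, so this only illustrates the order of size. Assume independent misses of 3% to 10% per dose, half the patients completing 35 further doses, and the planned 50% dropout spread evenly over 0 to 34 doses. A run of two or more misses followed by a dose then occurs in 2.1% to 19.4% of patients, and of three or more in 0.06% to 2.06%. Those are shares of patients with a gap, not of affected films.

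For an affected film, a radiograph must also fall in days 91 to 120 and before the restart. With the ±7-day shift, that window averages about 2.07 days for two missed doses, 28.5 for three and 30 for four. Assume one film a year at a random time. At 10% misses the expected runs per patient are about 0.196 of exactly two, 0.0188 of three and 0.0018 of four (longer runs add little), so

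(0.196 × 2.07 + 0.0188 × 28.5 + 0.0018 × 30) ÷ 365.25 ≈ 0.0027 films per patient.

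At 3% misses the same sum gives about 0.00016. For the 500 planned patients that is 500 × 0.00016 ≈ 0.1 to 500 × 0.0027 ≈ 1.4 films. Misses that cluster within patients would raise it.

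**The case against.** The strongest objection is that the link is inferred. In section 5.4 the asterisk pointing to section 5.5 is on the end date, not on interruption. The 90-day rule already stood in SAP v4.0 and v4.1, when section 5.5 had no interruption variable. The interruption row copies the dosing-interval row, down to saying that the dosing interval is missing, so a drafting slip is plausible. With a monthly drug, interruption could be read as starting at the first missed dose, about 30 days after the last one taken, which would align the rules. The separate data set specifications, which are not available here, may settle it.

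The inference has to be stated, and it limits confidence. It does not remove the conflict. The variable was added in v5.0, is the SAP's only definition of interruption length, and no analysis in section 6 tabulates it, so serving the 90-day rule is its evident purpose. The first-missed-dose reading is not what the formula says; if it was meant, the formula needs the correction proposed here. Applying the 90-day rule to patients who never restart does not help either: 90 days always comes before 120, so the stated 90-day allowance could never operate.

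It is also fair that nothing requires the shared limit to be 120 days. Counting both rules from the last dose would align them at 90. The case for 120 is that it follows the existing end-date and treatment-duration definitions.

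Three stronger readings are not supported:
- A reader might cite a patient who restarts before the film and loses it while back on drug. That loss comes from the rule that drops everything after a triggering gap, and exposure before the film differs, so it does not show this inconsistency.
- A reader might take 2.1% to 19.4% as the share of patients affected. It is an assumed share with a run of missed doses.
- A reader might infer that non-vertebral fracture has no rule. Section 5.4 covers it among the other endpoints. Section 6.3.2 says "Non-vertebral fracture will be analyzed in the same manner as described in Section 6.3.1" but sets its own censoring dates, so the wording needs clarifying and no more.

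**Conclusion.** The inconsistency is real and should be corrected. On the SAP's own formulas, the limits for vertebral radiographs, bone density and height are 120 and 90 days after the last dose, and the 30 days between them are decided by later dosing. This rests on one inference, that the section 5.5 variable drives the 90-day rule; confidence is medium for that reason.

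The practical effect is probably small. The number of films cannot be computed from the documents, and neither can any effect on a fracture, bone density or height estimate; the illustration of about 0.1 to 1.4 films rests wholly on assumed rates. The documents do not support calling the primary result materially biased. What they support is that inclusion of a primary-endpoint film should not turn on events after it, and that the repair is cheap.

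**What to change.** For vertebral radiographs, bone mineral density and height, define interruption as the next dosing date minus (previous dosing date + 30 days), set to 0 if negative. Both rules then stop at 120 days after the last dose taken. Apply it in sections 5.4, 5.5, 6.3.1 (text and note *1) and 6.3.3.

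Do not simply edit the shared variable. The interruption rule covers all efficacy analyses, so that edit alone would move bone turnover markers and low back pain from 60 against 90 days to 60 against 120 and double their window of disagreement from 30 to 60 days. Either create an endpoint-specific variable or reconcile those two endpoints in the same revision.

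As clarifications only, state whether the limit is at least 90 or more than 90 days, unless the data set specifications already do, and say in section 6.3.2 which interruption formula, if any, applies.

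The work is one or two derived variables, matching text and a rerun. Two consequences should be stated: up to 30 more days without dosing are kept for patients who resume, and the trigger moves from about two to about three missed monthly doses. Any selection on adherence from dropping all data after a triggering gap is left as it is.
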